12.3.4. Quality of Life Assessment – Inflammatory Bowel Disease Questionnaire

The IBD-Q is a 32 item questionnaire validated to measure quality of life in CD and UC. The IBD-Q assesses the dimensions of bowel function, emotional status, systemic symptoms and social function ([Guyatt G, 1989](#)). The IBD-Q will be completed by all subjects at screening (Visit 1), before dosing (Visit 2), and at the end of the open-label treatment period or early termination (Visit 10/ET) (see [Table 1](#)).

13. STATISTICS

Detailed descriptions of data summaries and listings will be provided in the Statistical Analysis Plan, which will be finalized prior to database lock. The sections below provide a summary of the planned statistical methods.

13.1. Statistical Methods

Pharmacokinetic, efficacy and quality of life data will be summarized with traditional descriptive statistics. Continuous variables will be summarized with N, mean, standard deviation, and range. Categorical variables will be summarized by frequencies and percentages.

No formal inferential analyses are planned.

13.1.1. Analysis Populations

The Safety Population will include all subjects who are enrolled in the study and receive any amount of investigational product. The Pharmacokinetic Population will include all subjects who received their assigned dose of MDGN-002 and for whom MDGN-002 plasma concentration data are available. The Efficacy Population will include all subjects who have a baseline and at least 1 post-baseline efficacy score.

13.1.2. Statistical Analyses

Analyses of efficacy will focus on the Efficacy Population. Results of endpoints (e.g., CDAI, SES-CD, abdominal pain and loose/watery stool frequency and IBD-Q (CD only; Modified Mayo Score, stool frequency, rectal bleeding, endoscopic appearance, and IBD-Q (UC only) will be summarized by visit for each cohort, both as raw scores and the change from baseline value. For CD, the CDAI individual and total scores will be derived programmatically using recorded data from patient diary, responses to CDAI questions, laboratory tests, and physical exam results.

For UC, the Modified Mayo Score individual and total scores will be derived programmatically using recorded data from patient diary and endoscopy results. Quantitative endoscopy and biopsy results will also be summarized for both the Baseline and End of study visits.

Analyses of safety data will be focused on the Safety Population (as defined in [Section 13.1.1](#)).

Safety variables include treatment-emergent AEs (TEAEs), clinical laboratory results, vital signs measurements, ECG results, and physical examination findings.

Adverse events will be coded using Medical Dictionary for Regulatory Affairs (MedDRA). TEAEs are defined as any AE having first onset or worsening in severity after the first administration of IP. TEAEs will be classified by system organ class (SOC) and preferred term and summarized by the number of subjects reporting each event for each cohort and overall.

For clinical laboratory tests, descriptive summaries of actual (absolute) values and change from baseline values will be presented by cohort for each study visit.

Vital signs (systolic and diastolic blood pressure, pulse, and respiratory rate) and ECG results will be summarized by visit and cohort using appropriate descriptive statistics.

Data in this open-label study will be monitored continually and may be analyzed at any time.

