Subjects who are currently taking a biologic treatment or who have received biologic treatment within 12 weeks of the Screening Visit but who are otherwise eligible for study participation based on review of all screening evaluations and results will begin a wash-out period for these medications. Washout is the period between when the subject received their last dose of biologic and when they are eligible to proceed to Visit 2. With the exception of subjects requiring wash-out of the biologic certolizumab pegol (Cimzia), a blood test will be administered to subjects undergoing wash-out 8 weeks after their last dose of biologic treatment to ensure that serum levels of any previous biologic treatments are below the level of detection. If it is confirmed that the levels of previous biologic treatment are undetectable, then the subject will proceed to Visit 2. If the test results indicate that the previous biologic treatment is detectable, the subject will be required to complete a full 12-week wash-out period before proceeding to Visit 2. For subjects receiving the biologic certolizumab pegol (Cimzia) a 12-week wash-out is required.

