12.3.1.6.2. Definition of Adverse Events, Period of Observation and Recording of Adverse Events

An AE is defined as any untoward medical occurrence in a clinical investigation subject administered a pharmaceutical product that does not necessarily have a causal relationship with the product. An AE can therefore be any unfavorable and unintended sign (including a new, clinically important abnormal laboratory finding), symptom, or disease, temporally associated with the product, whether or not related to the product.

All AEs are collected from the time of the informed consent is signed until the final safety follow-up visit (described in [Section 8.2.3](#)). This includes events occurring during the screening phase of the study, regardless of whether investigational product is administered. Where possible, a diagnosis rather than a list of symptoms should be recorded. If a diagnosis has not been made, then each symptom should be listed individually. All AEs should be captured on the appropriate AE eCRF and in source documents. In addition to AEs, unexpected benefits outside the investigational product indication should also be captured in the source documents and AE eCRF.

All AEs must be followed to closure (ie, the subject’s health has returned to his/her baseline status or all variables have returned to normal), regardless of whether the subject is still participating in the study. Closure indicates that an outcome is reached, stabilization is achieved (the investigator does not expect any further improvement or worsening of the event), or the event is otherwise explained. When appropriate, medical tests and examinations are performed so that resolution of an event(s) can be documented.

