NOTE: Medical and scientific judgment should be exercised in deciding whether it is appropriate to consider other situations serious, such as important medical events that may not be immediately life-threatening or result in death or hospitalization but may jeopardize the subject or may require intervention to prevent one of the other outcomes listed in the definition above. Examples of such events are intensive treatment in an emergency room or at home for allergic bronchospasm, blood dyscrasias or convulsions that do not result in hospitalization, or development of drug dependency or drug abuse.

12.3.1.6.6.3. Serious Adverse Event Collection Time Frames

All SAEs, regardless of the relationship to study, are collected from the time the subject signs the informed consent until the subject's last visit (office or telephone contact). The investigator or designee must report all SAEs promptly to the CRO and Aevi Genomic Medicine medical monitor within 24 hours of first becoming aware of the event.

Any SAE(s), regardless of relationship to IP, discovered by the investigator at any interval after the study has completed must be reported to the CRO and Aevi Genomic Medicine medical monitor within 24 hours of the first awareness of the event.

12.3.1.6.6.4. Serious Adverse Event Onset and Resolution Dates

The onset date of the SAE is defined as the date the event meets serious criteria (see [Section 12.3.1.6.6.2](#)). The resolution date is the date the event no longer meets serious criteria, the date symptoms resolve or the event is considered chronic. In the case of hospitalization, the hospital admission and discharge dates are considered respectively, the onset and resolution dates of the SAE.

Any signs or symptoms experienced by the subject after signing the informed consent form, or leading up to the onset date of the SAE or following the resolution date of the SAE must be recorded as AEs.

12.3.1.6.6.5. Fatal Outcome

An outcome of “fatal” should only be selected when the AE results in death. If more than 1 AE is possibly related to the subject’s death, “fatal” outcome should be indicated for each such AE.

Any AE that results in the subject’s death must have “fatal” checked as an outcome with the date of death recorded as the resolution date. Adverse events resulting in death must be reported within 24 hours as SAEs, if not already reported as such.

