6.1.2 Safety Analysis Set

The Safety Analysis Set will include all subjects who are enrolled and receive at least one dose of study drug.

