9.2 ADVERSE EVENTS

Any untoward medical event that occurs after signing the informed consent form (ICF) is considered to be an adverse event (AE). Adverse events recorded between the time of signature of informed consent until the first dose administration will be considered baseline signs and/or symptoms.

A treatment-emergent adverse event (TEAE) is an adverse event with onset on or after the first dose administration date or an adverse event present before the first dose administration date that worsens (i.e., increases in severity) on or after the first dose administration date. TEAEs will be summarized from the first dose administration date through:

- the Safety Follow-Up/Visit 11 for subjects who completed the study or
- 28 days after the last dose administration date for subjects who discontinued prematurely from the study.

Verbatim terms used by investigators to identify AEs in the CRFs will be coded to the appropriate preferred term (PT) and system organ class (SOC) using a standardized coding dictionary (MedDRA Version 23.0 April 2020). All coding will be reviewed prior to database lock. All recorded AEs will be listed, but only TEAEs will be summarized.

Adverse events will be classified according to severity (CTCAE Grades 1-5) and relationship to study drug (not related, possibly related, or probably related). For summary tables, a "related" adverse event is one judged to be possibly related or probably related to study drug.

The following adverse event categories will be summarized by disease and cohort:

- Overall TEAEs
- TEAEs related to study drug
- TEAEs leading to discontinuation
- Serious AEs
- Severe TEAEs (Grade 3 or higher)

The number of subjects with AEs will be further summarized by SOC and PT (TEAEs, as well as related TEAEs), by PT only, and by SOC, PT and severity. Sorting will be in descending order of frequency.

If a patient has multiple occurrences of a TEAE within the same SOC and PT, only the most related or most severe will be included in the summaries.

Separate listings for all AEs, serious AEs, and AEs leading to discontinuation will be generated.

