15.2 LISTINGS

Listing Number	Analysis	Title
	Set	

16.2.1.1	All Subjects	Subject Disposition
16221		Subjects Not Meeting Inclusion / Meeting
16.2.2.1	All Subjects	Exclusion Criteria
16.2.2.2	All Subjects	Protocol Deviations
16.2.3	All Subjects	Study Populations
16.2.4.1	Safety	Demographics and Baseline Characteristics
16.2.4.2.1	Safety	Medical History
16.2.4.2.2	Safety	Crohn's Disease History
16.2.4.2.3	Safety	Ulcerative Colitis History
16.2.4.3	Safety	Prior and Concomitant Medications
16.2.5.1	Safety	Drug Administration and Accountability
16.2.5.2	PK	Pharmacokinetic Sample Collection and Concentration
16.2.5.3	Safety	Anti-drug Antibodies (ADA)
16.2.6.1.1	FAS	Quantitative Endoscopy (SES-CD) and Biopsy – Part 1
16.2.6.1.2	FAS	Quantitative Endoscopy (SES-CD) and Biopsy – Part 2
16.2.6.2.1	FAS	Modified Mayo Score for Ulcerative Colitis
16.2.6.2.2	FAS	Ulcerative Colitis Subject Diary
16.2.6.3.1	FAS	Crohn's Disease Activity Index (CDAI) Scores
16.2.6.3.2	FAS	Crohn's Disease Subject Diary
16.2.6.3.3	FAS	Crohn's Disease Activity Index (CDAI) Non- Diary Item Data and Related Questions
16.2.6.4	FAS	Inflammatory Bowel Disease Questionnaire (IBD-Q)
16.2.7.1	Safety	Adverse Events
16.2.7.2	Safety	Serious Adverse Events
16.2.7.3	Safety	Adverse Events Leading to Discontinuation
16.2.8.1	Safety	Hematology Laboratory Results
16.2.8.2	Safety	Serum Chemistry Laboratory Results
16.2.8.3	Safety	Fecal Chemistry Laboratory Results
16.2.8.4	Safety	Urinalysis Laboratory Results
16.2.8.5	Safety	LIGHT and Confirmatory Disease Biopsy Results
16.2.8.6	Safety	Other Laboratory Results
16.2.9.1	Safety	Vital Sign Measurements
16.2.9.2	Safety	Physical Examination
16.2.9.3	Safety	12-Lead Electrocardiogram (ECG)

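### The SAP undertakes to list every recorded adverse event, but its index places the AE and SAE listings on dosed subjects only

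*Protocol*

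**What the plan says.** **Collection.** Protocol section 12.3.1.6.2 starts adverse event collection at consent and adds: "This includes events occurring during the screening phase of the study, regardless of whether investigational product is administered". For serious events, section 12.3.1.6.6 says: "All SAEs, regardless of the relationship to study, are collected from the time the subject signs the informed consent".

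**Wash-out.** Under Protocol section 8.2.1, otherwise eligible subjects who are on a biologic, or had one within 12 weeks of screening, "will begin a wash-out period for these medications". The opening of Protocol section 12 places consent before prohibited therapy is stopped.

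**Safety set.** Protocol section 13.1.2: "Analyses of safety data will be focused on the Safety Population". Protocol section 13.1.1: "The Safety Population will include all subjects who are enrolled in the study and receive any amount of investigational product". SAP section 6.1.2: "The Safety Analysis Set will include all subjects who are enrolled and receive at least one dose of study drug". SAP section 9.1 makes this set the default for safety analyses and allows stated exceptions.

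**Listings.** SAP section 9.2: "All recorded AEs will be listed, but only TEAEs will be summarized". The index in SAP section 15.2 then carries the row "16.2.7.2 Safety Serious Adverse Events", and Listing 16.2.7.1 for all adverse events has the same assignment.

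**The concern.** The primary objective is safety and tolerability, and the adverse event listings are where a reader of the study report would look for every recorded harm. The plan deliberately collects events in people who may never be dosed, and section 9.2 undertakes to show them. The index then assigns the listings to a set that excludes those people.

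What is at stake is completeness of harms reporting. Stopping a biologic and undergoing a screening endoscopy with biopsy are things the study can ask of a person before any study drug is given. If such a person has a flare, a complication or a hospital admission and is then not dosed, a programmer working from the index would leave the event out of both listings. With about 14 subjects planned, one such serious event would matter to a reader.

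**Working it through.** No formula applies and the plan gives no figure to reproduce. The check is whether four parts of the plan fit together.

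**Step 1. Will there be adverse event records in never-dosed subjects?** Yes. Collection starts at consent and does not depend on dosing (Protocol sections 12.3.1.6.2 and 12.3.1.6.6). Sections 12.1.2 and 12.1.3.1.1 also tell sites to record new adverse events in a subject found ineligible before removing that subject from screening. SAP section 5.7 foresees such records, because it rules out date imputation for subjects who did not receive study drug.

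**Step 2. Can those subjects be in the Safety set?** No. Both definitions require enrolment and receipt of study drug. SAP section 6.2 defines enrolled subjects as those who are not screen failures, so a subject removed during wash-out fails on both counts.

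**Step 3. Does SAP section 9.2 cover them?** On its wording, yes. It counts any untoward event after consent as an adverse event. It treats events before the first dose as baseline signs or symptoms, which keeps them out of the treatment-emergent summaries. The sentence on listing covers all recorded events.

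**Step 4. Which set does the index assign?**

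| Adverse event outputs in SAP 15.1 and 15.2 | Number | On Safety set | On All Subjects |
|---|---|---|---|
| Tables 14.3.2.1 to 14.3.2.5 | 5 | 5 | 0 |
| Listings 16.2.7.1 to 16.2.7.3 | 3 | 3 | 0 |
| Total | 8 | 8 | 0 |

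The index does use All Subjects elsewhere: for Table 14.1.1 (disposition) and for Listings 16.2.1.1, 16.2.2.1, 16.2.2.2 and 16.2.3 (disposition, eligibility, protocol deviations, study populations). That is 1 + 4 = 5 outputs, none of them for adverse events. As indexed, a never-dosed subject's protocol deviation would be listed and the same subject's serious adverse event would not.

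**Step 5. Who is affected?**

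| Event | Under 9.2 | Under the 15.2 index |
|---|---|---|
| After first dose | Listed; summarized if treatment-emergent | Same |
| Before first dose, subject later dosed | Listed | Listed |
| Subject never dosed | Listed | Not listed |

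Only the last row conflicts.

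**The case against.** The strongest reply is that SAP section 9.1 allows exceptions and section 9.2 states one. On that reading the body text already covers never-dosed subjects, section 5.7 supports it, and the only error is a label in the index. This is a fair reading, and for that reason the omission cannot be called settled. But it concedes that the label is wrong, and the index is the only place where a population is assigned to each listing. The two sections still have to be reconciled.

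Second, the objective concerns the safety of the study drug, and events in unexposed people cannot inform it. That stands for the treatment-emergent tables, which rightly stay on dosed subjects. It does not answer the undertaking in section 9.2.

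A reader might also infer more than the documents support:

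- *That Protocol section 13.1.2 itself bars undosed subjects.* It says only that safety analyses focus on the Safety Population. The restriction on the listings comes from the SAP default and the index.
- *That the data are lost.* They are not. Events are recorded in the case report form, serious events go to the sponsor within 24 hours, and investigators review safety data weekly. The gap is in the planned report outputs.
- *That more than half of the observation time is dropped*, from 14 weeks of screening against 12 weeks from Day 0 to Day 84: 14/(14 + 12) = 54%. This does not measure loss. Pre-dose events of dosed subjects are listed, and a never-dosed subject has no post-dose period to set against it. Fourteen weeks is also a ceiling: wash-out counts from the last biologic dose, so part can precede consent; it can end at 8 weeks; and some subjects need none.
- *That the omission selects the subjects who worsened.* This is plausible, since a change in background medication could break the stable-dose conditions in Protocol section 10.2.1. But no criterion makes worsening itself a bar to Visit 2: the endoscopic score for Crohn's disease has only a lower limit, and the ulcerative colitis range runs to the scale maximum of 9.
- *That requiring at least one dose (SAP) rather than any amount of product (Protocol) would exclude a subject whose first injection was interrupted.* Nothing in the SAP defines a dose as a complete dose.

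**Conclusion.** The concern holds as an internal contradiction in the SAP: section 9.2 promises a complete listing and the section 15.2 index does not deliver it. If the index is followed, adverse and serious adverse events in subjects who consented but were never dosed appear in no adverse event output.

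The size in subjects cannot be given, because the documents do not state how many would be screened or washed out and then not dosed. No treatment-emergent summary and no numerical result changes. This is a small correction, but it decides whether the harms listings are complete.

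The conclusion assumes that programmers take each listing's population from the index. It also assumes that All Subjects means everyone screened. SAP section 6.1 does not define that label, but the disposition table that carries it counts subjects screened and screen failures.

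**What to change.** Before the SAP is signed off:

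- In section 15.2, change the analysis set of Listings 16.2.7.1 and 16.2.7.2 from Safety to All Subjects.
- Identify never-dosed subjects in both listings.
- In section 9.2, state that these two listings are an exception to the section 9.1 default.
- Keep Tables 14.3.2.1 to 14.3.2.5 on the Safety set, since a treatment-emergent event requires a first dose.

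Listing 16.2.7.3 can stay as it is, because the protocol treats ineligible subjects as removed from screening and the SAP counts screen failures separately from study discontinuations. No wash-out flag or change to the Safety set definition is needed.

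The data are already collected. The cost is two index entries, one sentence, one identifier in the listings and slightly longer output.

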13.2. Sample Size Determination

This is the first use of MDGN-002 in the intended population of patients with CD or UC resistant to anti-TNF α monoclonal antibodies. The sample size of the study was based on feasibility.

14. STUDY CONDUCT

Steps to ensure the accuracy and reliability of data include the selection of a qualified investigator and appropriate study site, review of protocol procedures with the investigator and associated personnel prior to the study, periodic monitoring visits, and meticulous data management.

14.1. Sponsor and Investigator Responsibilities

14.1.1. Sponsor Responsibilities

The sponsor is obligated to conduct the study in accordance with strict ethical principles ([Section 16](#)). The sponsor reserves the right to withdraw a subject from the study ([Section 9.6](#)), to terminate participation of a study site at any time ([Section 14.5](#)), and/or to discontinue the study ([Section 14.4](#)).

Aevi Genomic Medicine agrees to provide the investigator with sufficient material and support to permit the investigator to conduct the study according to the study protocol.

14.1.2. Investigator Responsibilities, Protocol Adherence and Investigator Agreement

By signing the Investigator's Agreement ([Appendix 18.1](#)), the investigator indicates that she/he has carefully read the protocol, fully understands the requirements, and agrees to adhere to the study procedures as detailed in this protocol. The investigator is responsible for enrolling only those subjects who have met the protocol eligibility criteria.

The investigator also agrees to conduct this study in accordance with all laws, regulations, and guidelines of the pertinent regulatory authorities, including and in accordance with the International Conference on Harmonisation (ICH) Guidance for Industry E6 GCP and in agreement with the Declaration of Helsinki. While delegation of certain aspects of the study to subinvestigators and study coordinators is appropriate, the investigator will remain personally accountable for closely overseeing the study and for ensuring compliance with the protocol and all applicable regulations and guidelines. The investigator is responsible for maintaining a list of all persons that have been delegated study-related responsibilities (e.g., subinvestigators and study coordinators) and their specific study-related duties.

The investigator should ensure that all persons who have been delegated study-related responsibilities are adequately qualified and informed about the protocol, investigational products, and their specific duties within the context of the study. The investigator is responsible for providing Aevi Genomic Medicine with documentation of the qualifications, GCP training, and research experience for themselves and their staff as required by the sponsor and the relevant governing authorities.

According to local laws and regulations, the investigator, sponsor or sponsor designee will communicate with the IRB to ensure accurate and timely information is provided throughout the study.

